4 SELECTION AND ENROLLMENT OF PARTICIPANTS

Sample Size and Population

Patients will be recruited from geriatric and primary care clinics in three different health systems. To ensure diversity in our study population, we have purposefully engaged health systems that have higher racial and ethnic minority patient populations from the surrounding area. One of our sites is a federally qualified healthcare center, which ensures oversampling for socioeconomic diversity.

While pilot studies typically do not warrant power calculations, a target sample size can be estimated to ensure the results support progression to a full trial. Based on Lewis et al's red zone/green zone criteria, with an anticipated proportion for the upper red zone cut-off of 40% and the lower green zone cut-off of 50% for a one-sample test and 80% power (Aim 1), we will aim to recruit 160 patients or patient-care partner dyads.

We will include dyads whenever feasible, but so as not to exclude isolated adults, many who may be from historically underrepresented groups, we will allow for individuals whose physicians determine they have the capacity to understand the intervention to also participate on their own. Given that clinicians would see these individuals in clinic on their own anyway, clinician determination of capacity to participate is a pragmatic approach. This means that we act under the assumption that patients who require a care partner will have already included them in previous visits and/or provider communications (and we anticipate that this will be documented in the EHR), whereas patients who attend clinic visits independently and have no documentation indicating the involvement of a care partner in their medical decisions, or a need for one, will be determined to have the capacity to also participate in a PPC visit. PPC is designed such that even those with MCI or early dementia can engage in meaningful discussions with their provider about their preferences.

Dementia and MCI

To identify individuals with dementia and MCI, we will use two or more instances of use of an ICD-10 code for either diagnosis in the EHR within 24 months. Typically, we would include instances of these billing codes within a year of each other, but due to the COVID-19 pandemic, we recognize that there may be less frequent clinical visits and less robust billing. We will use the following billing codes: F01.50, F01.51, F02.80, F02.81, F03.90, G30.0, G30.1, G30.8, G30.9, G31.01, G31.09, G31.1, G31.2, F41.81, G31.84 and F03.91.

Health Equity

To ensure diversity of our study population, we have purposefully engaged health systems that have higher racial and ethnic minority patient populations than the surrounding area. Furthermore, one of our sites is at a Federally Qualified Healthcare center, which ensures oversampling for socioeconomic diversity. Purposeful oversampling such as this is a well-established method for ensuring a strong signal in research data from underrepresented groups.

4.1 Inclusion Criteria

Patient Inclusion Criteria

Patients must meet all of the following criteria to participate in this study:

- 40 years or older
- English-speaking
- Receiving care with a participating physician
- Has a scheduled outpatient care visit within 1-2 months (60 days)
- Individual has a diagnosis of MCI or dementia

Definition: To identify individuals with dementia and MCI, we will use two or more instances of use of an ICD-10 code for either diagnosis in the EHR within 24 months. Typically, we would include instances of these billing codes within a year of each other but, due to the COVID-19 pandemic, recognize that there may be less frequent clinical visits and less robust billing. Diagnostic codes include:

- F01.50, F01.51, F02.80, F02.81, F03.90, G30.0, G30.1, G30.8, G30.9, G31.01, G31.09, G31.1, G31.2, F41.81, G31.84 and F03.91.

Care Partner Inclusion Criteria

Care partners must meet all of the following criteria to participate in the study:

- 18 years or older
- English-speaking

A note about inclusion of care partners: Clinician determination of a patient's capacity to participate in a visit independently is part of a pragmatic approach. This means that clinic staff will determine when a care partner is needed. Generally, we act under the assumption that patients who require a care partner will have already included them in previous visits and/or provider communications (and we anticipate that this will be documented in the EHR), whereas patients who attend clinic visits independently and have no documentation indicating the involvement of a care partner in their medical

decisions, or a need for one, will be determined to have the capacity to also participate in a PPC visit.

4.2 Exclusion Criteria

Participants who meet any of the following criteria will be excluded from the study:

- Is not community-dwelling- e.g. lives in a nursing home
- Is enrolled in hospice
- Individuals who decline to receive the PPC intervention (i.e. decline to have the PPC conversation) will be excluded from the study.
 - Note that declining to receive the PPC intervention will in no way impact the care that patients receive now or in the future.

4.3 Study Enrollment Procedures

Patients will be identified by research staff using the EHR and other administrative data provided by the participating clinical site. The EHR will be accessed by research staff at each clinical site. Clinic schedules will be reviewed to identify patients with upcoming appointments who meet criteria for inclusion. Providers may also notify research staff if they are aware of an upcoming appointment with an individual who would be eligible for PPC.

Providers and facilitators will be notified when patients have been mailed a PPC packet via their preferred method of communication (ex: EHR or other secure messaging). They will not be responsible for pre-screening patients for inclusion in this mailing.

Recruitment efforts will be recorded by research staff at each clinical site in a screening log. Reasons for exclusion will be tracked.

5 STUDY INTERVENTIONS

5.1 Interventions, Administration, and Duration

The PPC intervention is comprised of an initial two-step process that can involve 1-2 clinic staff:

1. *Priorities identification* with a facilitator prior to seeing their physician or advanced practice provider(s) either: 1-2 weeks prior to or in tandem with the outpatient clinic visit.
2. *Alignment of patient priorities with their medical care plan* in collaboration with their clinician (typically a physician or advanced practice provider). Consistent with local clinical practices, the facilitator and clinician will be identified by clinic leadership for each eligible participant.

A facilitator for the first step of the intervention may be any member of the clinical team. The clinician in the second step must be the patient's physician or advanced practice provider.

5.2 Handling of Study Interventions

Following training of facilitators and providers, the research team will begin to review the

clinic schedule to identify individuals that qualify to receive the PPC intervention, based on the inclusion criteria provided.

The **intervention** will consist of the following steps:

1. Research staff will provide the PLWDM with information about PPC in a paper format with instructions to access materials in an electronic format. The paper packet will be mailed to the patient approximately 1-4 weeks prior to their next clinic visit, Electronic materials will be available online (myhealthpriorities.org). These materials will not include information about the patient's medical history or any other protected health information. No identifiable participant information will be stored on the electronic site.
 - The research team will notify facilitators and clinicians via the EHR or secure messaging to indicate which patients have been mailed a PPC packet. The method of notification will be determined based on the provider's preference.
2. Facilitators will determine the best method to engage with patients based on clinical environment and information found in the EHR. They will use clinical judgment to determine when and how to engage care partners during this step. Options might include:
 - phone calls to patients and/or care partners 1-2 weeks prior to the next clinic appointment
 - engage in discussion about the PPC packet
 - encourage the patient and/or care partner to complete the worksheet
 - engaging in PPC discussions on the day of the appointment in tandem with the clinician visit but prior to seeing the clinician
3. Research staff will send patients electronic nudges (reminders through the patient portal) approximately one to five day(s) prior to their clinic visit to engage in PPC goal setting and bring any necessary materials to their clinic visit. These nudges will be sent as clinical reminders on behalf of the clinic staff, using the electronic patient portal, and will be automated when possible.
4. Staff will provide a reminder about PPC to the patient and/or care partner, using an integrated approach during the clinic check-in workflow, in which check-in staff will provide the patient and/or care partner with a PPC packet. Research staff will provide a reminder in the EHR appointment note to alert clinic check-in staff about patients that should receive a PPC packet. These packets will be prepared and delivered (or mailed) to each clinic, by research staff.
5. Patient EHR records will be evaluated for two years prior to the clinic visit for purposes of ascertaining eligibility and suitability to engage in PPC. Other data will be collected from the patient's medical record for two years prior to the clinic visit and outcomes data will be collected for two months after the clinic visit.

PEP Talks (Perspectives on Embedded Patient Priorities Care Talks) Interviews

Semi-structured, audio-recorded participant interviews will also be conducted with a selection of facilitators, clinicians, patients, and care partners. These interviews will be conducted between 1 day and 3 months of the clinic visit. We will oversample for

minority representation for these interviews. We anticipate completing interviews with up to approximately 30 participants. Participants will be offered a \$20 incentive for completing this interview.

5.3 Concomitant Interventions

5.3.1 Allowed Interventions

Not applicable

5.3.2 Required Interventions

Not applicable

5.3.3 Prohibited Interventions

Not applicable

5.4 Adherence Assessment

Documentation of PPC discussion in 35% of eligible participants in the EHR will be ascertained using a Natural Language Processing (NLP) model. Participating clinicians will be trained to utilize the vendor “dot phrases” (pre-defined, templated language or EHR equivalent) to prompt the beginning of their PPC documentation. These dot phrases will then be incorporated into the NLP model to identify when PPC is documented within the clinical text. The NLP model will be trained to identify the dot phrases and extract details related to words following the phrase. For example: “patient care priorities were discussed, and patient wishes to...” A common script for identification of these dot phrases will be developed by the primary site and shared with the secondary site for local implementation. For the site that utilizes a different EHR vendor, a similar model will be employed ensuring the clinicians are trained to utilize similar language or programmatically input the equivalent of dot phrases. This will ensure the NLP model identifies the documentation.

6 STUDY PROCEDURES

6.1 Schedule of Study Steps

Study Steps	Screening: Pre-Visit (up to 8 weeks prior)	Outreach: Pre-Visit (1-4 weeks prior)	Outreach: Pre-Visit (1-2 weeks prior)	Outreach: Pre-Visit (1-5 days prior)	Intervention : Visit 1 (Day 0)	Follow-up: Post-Visit (2 months post visit)	Follow-up: Post-Visit (up to 3 months post visit)
Inclusion/Exclusion Criteria	X						
Mail PPC packet		X					
Review PPC packet			X				
Care partner assessment			X				
Send reminder (nudge) to patients			X	X			
Send nudge to facilitators and clinicians (per clinic preference)			X	X	X		
Provide PPC Packet at check-in					X		
Facilitator PPC Conversation (Step 1)			X		X		
Provider PPC Care Alignment (Step 2)					X		
Patient EHR/chart review	X				X	X	
Adverse Events					X	X	
Semi-structured qualitative interview (PEP Talks)							X

*Consistent with clinical practice the research team will have the ability to contact clinic staff by email, phone, EHR messaging, or other secure messages as needed to communicate about patients and/or care partners who are eligible for PPC.

6.2 Description of Evaluations

6.2.1 Screening Evaluation

These evaluations occur to determine if the candidate is eligible for the study.

Consenting Procedure

We will apply for a waiver of informed consent for most participants in this study because the intervention will be embedded within the standard clinical procedures.

A subset of clinicians and patients and care partners will experience traditional informed consent in order to participate in semi-structured, audio-recorded interviews with research staff as part of qualitative data collection. See Section 5.2 (PEP Talks) for details.

Screening

Trained research staff at each clinical site will conduct screening via the EHR and clinic schedule up to approximately 8 weeks prior to the clinic visit. Inclusion and exclusion criteria will be verified by research staff via the EHR by looking back in the patient's record for up to 2 years prior to the scheduled clinic visit. This review will occur up to 2 months prior to the patient's scheduled clinic visit. Screening and list generation will be automated where feasible.

6.2.2 Enrollment, Baseline, and/or Randomization

Enrollment

Due to the nature of the PPC model, there is no formal enrollment procedure or baseline research interview. Rather, patients will be considered enrolled if they meet inclusion criteria and a PPC packet is mailed to them.

- Note: a patient may decline to participate in the PPC intervention at any time. Declining to receive the PPC intervention will in no way impact their clinical care that patients receive now or in the future.
 - Individuals who inform their provider or other clinical staff that they wish to decline to receive the PPC intervention will be excluded from the enrolled patient list and will not be included in outcomes assessments for the study.

Baseline Assessments

The clinic visit is the reference point by which we will assess patient outcomes.

The PPC conversation will include two steps:

1. Priorities identification with a facilitator
2. Alignment of patient priorities with their medical care plan in collaboration with their physician or advanced practice provider(s).

Consistent with local clinical practices, the facilitator and clinician will be identified by clinic leadership for each eligible participant. A facilitator for the

first step of the intervention may be any member of the clinical team. The clinician in the second step must be the patient's physician or advanced practice provider.

Because the primary outcome is documentation in the EHR, the assessment for documentation will occur approximately two months (60 days) after the patient's clinic visit.

Randomization

Not applicable

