7.2.1 Reporting Procedures

The content of the data and safety monitoring report will include study status, recruitment, enrollment, and retention information and participant descriptive information. Safety and quality information will be reported using study quality reports for Co-PIs that will contain:

- Summary of adverse events, participant descriptive information, and an explanation of how each event was handled,
- Summary of complaints and how each complaint was handled,
- Subject retention, including the number and reasons of participant withdrawals,
- Summary of protocol violations and how each was handled. Reports will be submitted to the IRB on an as-needed basis.

All adverse events will be initially judged by the PI ([name]) based on three criteria:

1. expectedness (expected, unexpected),
2. relatedness to participation in the study (definitely related, possibly related, not related), and
3. severity (mild, moderate, severe).

These judgments will be circulated to the study team and reported to the Program Official as noted below.

- All **adverse events that are serious (SAE) and unexpected** (i.e., have not been previously reported for the study's intervention) will be reported to the IMPACT Collaboratory Regulatory and Data Team Leader ([name]), NIA IMPACT Collaboratory PO ([name]), and the IMPACT Collaboratory project's Safety Officer (SO) within 48 hours of the study's knowledge of SAE.
 - Only those adverse events that are serious (SAE), unexpected, **and related to the intervention** must also be reported to Advarra IRB. Unexpected and **unrelated** SAEs will be reported to Advarra IRB on a case-by-case basis if requested by the IMPACT Collaboratory project's Safety Officer (SO) or NIA IMPACT Collaboratory PO.
- All deaths will be reported to IMPACT Collaboratory Regulatory and Data Team Leader ([name]), NIA IMPACT Collaboratory PO ([name]), and the IMPACT Collaboratory project's Safety Officer (SO) within 24 hours of study's knowledge of death.
 - Advarra IRB does not require the specific reporting of death outside of the SAE reporting requirement above, but they will be notified on a case-by-case basis if requested by the IMPACT Collaboratory project's Safety Officer (SO) or NIA IMPACT Collaboratory PO.

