9.4.2 Secondary (implementation) outcomes

1. Identification of care partners for 50% of eligible PLWDM,
 - To meet green zone criteria, we must identify care partners for 50% of eligible PLWDM.
 - The red zone threshold is 40%.
 - Should the sample fall in the amber zone between 40-50%, then we will determine whether acceptable amendments can be made to the protocol to warrant progression to a full ePCT.

2. Documentation of PPC discussion in 35% of eligible participants in the EHR, which will be ascertained using an established Natural Language Processing model,
 - To meet green zone criteria, we must identify PPC discussion in 35% of eligible participants. In the original study of PPC, 66.3% of visit notes indicated a PPC discussion. Because that was performed at a single institution under ideal conditions, we expect that our pragmatic pilot will have a lower recruitment rate for this aim than the original study. That said, the 65% green zone is associated with a sample size of 159 individuals, which would include our overall recruitment goal.
 - Should the sample fall in the amber zone between 25-35%, then we will determine whether there are amendments that can be made to the protocol to warrant progression.
3. Evaluation of implementation endpoints (acceptability, appropriateness, feasibility, fidelity, and potential for future adoption of the intervention) assessed through chart review and semi-structured participant interviews with some patients, patient-care partner dyads, facilitators, and clinicians (Table 1).

If themes emerge that indicate potential future successful full ePCT, then this will meet progression criteria.

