We will use findings from Aim 3 to examine key feasibility measures across racial, ethnic, and socioeconomic subgroups to determine further adjustments that may be needed to tailor the intervention to a diverse population. We recognize that a “one size fits all” approach is inappropriate for many historically and structurally marginalized groups and that adjustments may need to be made to the flexibility of the overall intervention protocol. This may include identification of additional implementation or clinical endpoints for examination. Progression criteria for this aim is that we are able to determine the key feasibility measures for a minimum of the +/- 10% proportion of racial, ethnic, and socioeconomic subgroups that mirrors the populations seen in each health system. We will also conduct between-group comparisons on our measure of PPC documentation between Black v. White and those with financial insecurity vs. none (small sample sizes will preclude analysis of Hispanic patients and those with housing instability). If there are significant differences, we will make further adjustments prior to embarking upon a Stage IV ePCT of this intervention.

Table 1. Implementation outcomes and data sources		
	Implementation outcomes	Source of data
Feasibility	Identification of sample Enrollment goals Feasibility of outcome ascertainment	Administrative data Qualitative interviews with clinicians, patients, and care partners NLP

Adoption	Utilization /intent to use	EHR Qualitative interviews with clinicians
Acceptability / appropriateness	Satisfaction with the intervention (content, delivery, credibility) Perceived usefulness and practicality	Qualitative interviews with clinicians, patients, and care partners
Fidelity	Adherence to implementation protocol Quality of implementation	Training records – completion /results- competency Checklist of adherence to protocol -EHR Qualitative interviews- barriers /facilitators to refine implementation strategy

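### Patients who tell staff they decline PPC are dropped after enrolment, which raises the documentation rate judged against the 35% green threshold by a factor of about 1/(1-d), where d is the share who actively decline

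*Protocol*

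**What the plan says.** - **Enrolment.** Under Protocol section 6.2.2, "patients will be considered enrolled if they meet inclusion criteria and a PPC packet is mailed to them". There is no formal enrolment step.
- **Declining, section 6.2.2.** A patient may decline at any time. Those who tell their provider or other clinic staff "will be excluded from the enrolled patient list and will not be included in outcomes assessments for the study". The same section describes EHR documentation as the primary outcome, assessed about 60 days after the visit.
- **Declining, section 4.2.** The exclusion criteria say the same: "Individuals who decline to receive the PPC intervention (i.e. decline to have the PPC conversation) will be excluded from the study".
- **When exclusions are checked.** Section 6.2.1 says "Inclusion and exclusion criteria will be verified by research staff via the EHR by looking back", up to about 8 weeks before the visit. Section 6.1 places this before the packet is mailed.
- **The criterion.** Section 9.4.2: "To meet green zone criteria, we must identify PPC discussion in 35% of eligible participants". The amber band is 25-35%.
- **Subgroups.** Section 9.4.2 adds: "We will also conduct between-group comparisons on our measure of PPC documentation between Black v. White". It also compares patients with and without financial insecurity. Significant differences would lead to adjustments before the Stage IV trial.
- **Records of refusal.** Section 4.3 says "Reasons for exclusion will be tracked" in a screening log. Section 7.2.1 puts "Subject retention, including the number and reasons of participant withdrawals" in the study quality reports.

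The SAP compares demographics between patients with and without a documented conversation. It does not define a denominator for the documentation rate.

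**The concern.** Declining is treated as an eligibility criterion, but it can only happen after the patient has been screened, mailed a packet and counted as enrolled. It is also closely tied to the outcome: a patient who refuses the conversation will rarely have one documented. Removing such patients takes non-events out of the denominator and leaves the numerator almost unchanged.

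Refusal is itself a feasibility and acceptability finding. Under the rule as written it cannot lower the documentation rate, and each refusal moves the rate towards green. Refusals are logged, but nothing in either document links the log to the figure compared with 35%.

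The Black v. White comparison has the same weakness. If refusal differs between groups, removing decliners can hide a difference in reach, which is the kind of difference section 9.4.2 wants to act on.

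**Working it through.** **Inputs.** From the Protocol: 160 patients or dyads identified as eligible, green at 35%, amber at 25-35% (précis; sections 9.2 and 9.4.2). Assumed, because the documents are silent: the decline share d, shown from 2% to 30%, and the share s of decliners who already have a documented discussion, shown at 0% and 10%.

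**The plan's own figure.** The 160 comes from the care-partner endpoint (40% v 50%, one-sample test, 80% power). A normal approximation with one-sided alpha of 0.05 (assumed; the Protocol states none) gives 151 without and 161 with continuity correction, and an exact binomial calculation gives 158. So 160 is reproduced. It serves here only as the number mailed; nothing below depends on its derivation.

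**Expected shift.** Let r be the documented share of all mailed patients. After decliners are removed the expected rate is (r - s·d)/(1 - d). With s = 0 this is r/(1 - d).

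**What a reported 35% means.** With s = 0, the share of mailed patients is 0.35 × (1 - d):

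| d | 2% | 5% | 10% | 20% | 30% |
|---|---|---|---|---|---|
| Factor 1/(1-d) | 1.020 | 1.053 | 1.111 | 1.250 | 1.429 |
| Share of mailed patients | 34.3% | 33.3% | 31.5% | 28.0% | 24.5% |

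A true rate of 30% reaches 35% when 1 - d = 0.30/0.35, so d = 14.3%. A true rate of 25%, the bottom of amber, reaches it at d = 28.6%.

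**Chance of green, 160 mailed.** With decliners kept, green needs 56 of 160. The exact binomial chance P(X ≥ 56) is 3.2% for r = 28% and 23.2% for r = 32%. With decliners removed, I drew patients into four cells (declined or not, documented or not) 1,000,000 times and counted green when the rate among non-decliners was at least 35%:

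| True rate r | s | d = 2% | 5% | 10% | 20% | 30% | Decliners kept |
|---|---|---|---|---|---|---|---|
| 28% | 0% | 4% | 7% | 16% | 50% | 86% | 3% |
| 28% | 10% | 4% | 5% | 10% | 27% | 56% | 3% |
| 32% | 0% | 27% | 36% | 55% | 88% | 99% | 23% |
| 32% | 10% | 25% | 31% | 44% | 72% | 92% | 23% |

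If decliners were documented as often as everyone else (s = r), the expected rate would not shift at all.

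**Subgroups (assumed rates).** Suppose 40% of non-decliners are documented in both groups, so the planned comparison shows no difference. With 10% v 5% declining, the shares of mailed patients are 0.40 × 0.90 = 36% and 0.40 × 0.95 = 38%. With 30% v 10% declining, they are 0.40 × 0.70 = 28% and 0.40 × 0.90 = 36%.

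**The case against.** **The denominator is not stated outright.** Section 9.4.2 speaks of eligible participants, and 160 are to be identified as eligible through the EHR. On that reading decliners might stay in, since section 6.2.2 removes them from the enrolled list, and enrolled is the term used for Aim 2. This is the weaker reading: section 4.2 excludes decliners from the study altogether, and section 6.2.2 removes them from outcomes assessments in the same section that names EHR documentation as the outcome. If it were the intended reading, the text would still need to say so.

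**The size rests on an unknown d.** This stands. Only patients who actively tell staff they decline are removed; those who ignore the packet stay in. Nothing in the documents supports 20-30%, and the large figures need d in that range together with a true rate inside amber. At 2-5% the effect is small. Equally, nothing shows that d is small.

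**The consequences are limited.** Also true. Amber leads to consideration of protocol amendments, not to a stop, and documentation is one of several progression criteria. This argues against a higher severity.

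**The rule is prespecified, refusals are logged, and removal respects the opt-out.** Prespecification rules out a hidden change, but it does not make the rate measure reach among eligible patients. The logs should allow the other rate to be recovered, yet no one is told to calculate it. The opt-out matters because consent is waived, and any fix must honour it. Documentation among non-decliners is a legitimate measure of clinician uptake, so it should be kept as a second figure.

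**Conclusion.** The concern holds and should be fixed. As written, the rule removes enrolled patients because of a later event that nearly determines the outcome, and it raises the documentation rate by about 1/(1-d). The factor is exact if no decliner has a documented discussion, and smaller if some declined after a documented facilitator talk.

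The direction follows from the text on its more natural reading. The size does not, because d is assumed: negligible to small at 2-5%, and enough at about 14-29% to carry a true rate of 30% down to 25% over the green line. The effect is confined to active decliners and to one criterion among several, and the amber band softens its consequence.

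**What to change.** In Protocol sections 4.2, 6.2.2 and 9.4.2:

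- Define the denominator of the documentation rate as all eligible patients mailed a packet.
- Count a decliner as not documented unless a PPC discussion was already documented when they declined. Record that yes/no, with the date, in the screening log when the decline is logged.
- Report the number of decliners, and give the rate without them as a sensitivity analysis.
- Use the same denominator for the Black v. White comparison and report declining by subgroup, only where the characteristic is already held from screening. Leave decliners out of the financial-insecurity comparison unless that status is already known.
- Keep decliners out of the clinical EHR outcomes, with no further chart review, so that the opt-out is respected.

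**Cost.** A protocol amendment with IRB review, because consent is waived and declining is the patient's opt-out, and two log fields (date of decline; discussion already documented, yes/no). The reported rate will be somewhat less favourable. The documents do not show whether enrolment is still open. If it has closed, the denominator should still be fixed in writing before the rate is read, and both rates reported as far as the existing log allows.
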